4.3 Interim analyses and data monitoring

After the final Week 56 visit, an interim analysis will be performed and a corresponding interim clinical study report (CSR) may be written. A final analysis and updated final CSR will be prepared once all data (through the safety follow-up (SFU) visit) have been collected.

In addition, an independent Data Monitoring Committee (DMC) will periodically review and monitor the safety data from this study and advise UCB.

Cardiovascular and Neuropsychiatric Adjudication Committees will also periodically review and monitor safety data from this study and advise UCB. Details will be provided in the DMC Charter and in the Adjudication Committee Charters.

Further details related to the DMC will be outlined in a separate analysis plan.

4.4 Multicenter studies

The center-by-treatment interaction will be tested by replacing region with center in the logistic regression model used for the sensitivity analysis (Section 8.1.3.5) and adding a center-by-treatment interaction term. In the model, center will be based on the original centers prior to pooling (see Section 3.7). However, if the model is unable to converge due to a low number of subjects at a given center, a pooling by center will be applied in order to allow the model to converge. If convergence still cannot be achieved, this analysis will not be performed. Detailed strategy in Section 3.7 will be applied in order to allow the model to converge.

4.5 Multiple comparisons/multiplicity

[figure not shown]
The statistical analysis of the co-primary efficacy variables and selected secondary efficacy variables will account for multiplicity and control the familywise Type I error rate at a 2-sided alpha level of 0.05 by using a fixed sequence testing procedure.

The hypotheses (H_1 , H_2 , H_3 , H_4 , H_5 , H_6 , H_7 , H_8 , H_9 , H_{10} , H_{11} and H_{12}) comparing bimekizumab vs. adalimumab will be tested at a 2-sided alpha level of 0.05.

The first 2 hypotheses (H_1 and H_2) will test whether bimekizumab is noninferior to adalimumab for the co-primary efficacy variables, PASI90 response at Week 16 and IGA response at Week 16. This evaluation of noninferiority will be tested at a 1-sided alpha level of 0.025 and will be based on a 1-sided 97.5% CI and a noninferiority margin of 10%. If noninferiority is achieved, the alpha will be passed to the next test in the sequence, allowing the testing procedure to proceed. The co-primary efficacy variables of PASI90 response at Week 16 and IGA response at Week 16 will then be evaluated for superiority relative to adalimumab at a 2-sided alpha level of 0.05, and testing will proceed only if superiority is achieved for both endpoints.

The hypotheses associated with the subsequent secondary efficacy endpoints are based on testing for superiority relative to adalimumab. See Figure 4-1 for details on this procedure.

Figure 4-1: Sequence of testing

Note: Calculations for H₁-H₉ are based on the combined Bimekizumab arms with the sample size of 300. * in H₁₀-H₁₂ indicated calculations are based on the Bimekizumab Q4W/Q4W arm only with sample size of 150.

BKZ=bimekizumab; H=hypothesis; IGA=Investigator's Global Assessment; PASI=Psoriasis Area Severity Index; Q4W=every 4 weeks

4.6 Use of an efficacy subset of subjects

The primary efficacy analysis (described in Section 8.1.2) will be repeated based on FAS and PPS as a sensitivity analysis.

4.7 Active-control studies intended to show equivalence

A non-inferiority margin of 10% has been selected as this is considered to be a clinically relevant difference that could influence the choice of interventions used to treat chronic plaque PSO.

4.8 Examination of subgroups

Subgroup analyses will be performed on PASI75/90/100 response rates and IGA, using by visit summaries only. The following subgroups for analysis will be determined using baseline data:

- Age (<40 years, 40 to <65 years, ≥65 years)

- Gender (male, female)
- Disease duration (<median, ≥median)
- Region (North America [Canada, USA], Western Europe [Germany], Central/Eastern Europe [Czech Republic, Hungary, Poland, Russian Federation], Asia/Australia [Australia, Republic of Korea, Taiwan])
- Weight (≤100 kg, >100 kg)
- BMI (<25 kg/m², 25 to <30 kg/m², ≥30 kg/m²)
- Prior systemic phototherapy or chemotherapy (yes, no)
- Prior biologic exposure (yes, no)
- Prior systemic therapy of any kind (yes, no)
- Baseline disease severity (PASI<20, PASI≥20)
- Antibody positivity (negative, positive)

Antibody positivity is the only subgroup that is not determined by Baseline data. It will be presented in a separate table.

The definition of prior systemic therapy of any kind is that if a subject received previous biologic therapy, previous systemic therapy (non-biologic), or previous systemic chemotherapy or phototherapy. Subjects who never received previous biologic therapy, previous systemic therapy (non-biologic), or previous systemic photochemotherapy or phototherapy will be classified as not receiving prior systemic treatment for psoriasis.

In addition, in order to assess whether an early response to treatment is predictive of response at later time points, subgroup analyses will be performed for the RS on PASI90/100 and IGA over time using the following early response subgroups:

- PASI75 responders (OC) at Week 4 (yes, no) to predict PASI90/100 and IGA (NRI) through initial and maintenance treatment period
- PASI90 responders (OC) at Week 16 (yes, no) to predict PASI100 (NRI) through maintenance treatment period

All summaries will be based on imputed data as appropriate and will include descriptive statistics only.

5 STUDY POPULATION CHARACTERISTICS

5.1 Subject disposition

Summaries of reasons for screen failures (for all subjects screened), disposition of subjects (for all subjects screened), disposition of analysis sets (for RS), disposition and discontinuation reasons through Week 24 (for RS) and through initial and maintenance treatment period (for BKZ Set), as well as the subjects who discontinued due to AEs up to Week 24 (for RS) and up to Week 56 (for BKZ Set) will be produced. The disposition of subjects for all subjects screened will include the number of subjects included in each analysis set (ES, RS, SS, FAS, BKZ Set, BKZ Week 24 Set, MS, PPS and PK-PPS) overall and by site.

A subject is considered to have completed the Week 16 initial treatment period if they have either completed the Week 16 visit or received study medication from Week 16 onwards. Similar for Week 24.

The following listings for subject disposition will be provided: subjects who did not meet study eligibility criteria (all subjects screened), subject disposition (all subjects screened), study discontinuation (RS), visit dates (RS), subjects excluded from efficacy analysis (RS).

5.2 Protocol deviations

A summary of number and percentage of subjects with an important protocol deviation (including a summary of subjects excluded from any analysis set due to important protocol deviations) by treatment group and through initial treatment period, through Week 24 and through initial and maintenance treatment period will be provided for the RS.

A by-subject listing of important protocol deviations will be provided.

6 DEMOGRAPHICS AND OTHER BASELINE CHARACTERISTICS

All summaries detailed in this section will be performed on the RS by treatment group. Summaries for demographics and other Baseline characteristics will also be repeated in SS and BKZ Set. If the SS and RS analysis sets are identical the summaries will not be repeated.

6.1 Demographics

Demographic variables will be summarized by treatment group and overall.

The following continuous variables will be summarized using descriptive statistics (number of subjects, mean, SD, minimum, median and maximum).

- Age at the time of study entry (years)
- Height (cm)
- Weight (kg)
- BMI (kg/m²)

BMI (kg/m²) will be calculated as:

$$BMI = \frac{\text{Weight (kg)}}{(\text{Height (m)})^2}$$

The following categorical variables will be summarized using frequency counts and percentages.

- Age group (18-<65, 65-<85, ≥85 years)
- Age group (≤18, 19-<65, ≥65 years)
- Age group (<40, 40-<65, ≥65 years)
- Body Weight (≤100kg, >100kg)
- BMI (<25 kg/m², 25 to <30 kg/m², ≥30 kg/m²)

- Gender
- Race
- Ethnicity

By-subject listings of demographics will be provided.

6.2 Other Baseline characteristics

Baseline characteristics (including Baseline clinical measures) will be summarized by treatment group and overall.

Generally, the following continuous variables will be summarized using descriptive statistics (number of subjects, mean, SD, minimum, median and maximum).

- Psoriasis Body Surface Area (BSA; %)
- Psoriasis Area and Severity Index (PASI) score
- Modified Nail Psoriasis Severity Index (mNAPSI) total score
- Modified Nail Psoriasis Severity Index (mNAPSI) total score for subjects with nail involvement (i.e. mNAPSI>0)
- Patient Global Assessment of Disease Activity (PGADA) for arthritis visual analogue scale (VAS) score
- Dermatology Life Quality Index (DLQI) total score
- Duration of disease (years)

Duration of disease (years) will be calculated as:

$$\text{Disease Duration} = \frac{(\text{Date of randomization} - \text{Date of onset of Plaque Psoriasis}^1)}{365.25}$$

¹If the date of onset of plaque psoriasis is partial, it should be imputed to the most recent feasible date (ie, last day of the month if only day is missing, or the last day of the year if day and month are missing). Note that if the date of randomization is missing then the duration of disease will be derived using the date of screening.

The following categorical variables will be summarized using frequency counts and percentages.

- Region (North America [Canada, USA], Western Europe [Germany], Central/Eastern Europe [Czech Republic, Hungary, Poland, Russian Federation], Asia/Australia [Australia, Republic of Korea, Taiwan])
- Country
- Duration of disease (<median, ≥median)
- Investigator's Global Assessment (IGA) score
- Baseline disease severity (PASI<20, PASI≥20)
- PGADA score (PGADA=0, PGADA>0)
- DLQI total score (DLQI=0, DLQI>0)

- Nail involvement (yes, no)
- Scalp involvement (yes, no)
- Palmoplantar involvement (yes, no)
- Prior biologic exposure (yes, no)
- Prior primary failure to biologic (yes/no)
- Prior anti-TNF therapy (yes, no)
- Prior phototherapy or chemotherapy (yes, no)
- Any prior systemic therapy (yes, no)
- PSD items: Pain, Itch, Scaling

Baseline nail, scalp, and palmoplantar involvement are based on the number of subjects achieving mNAPSI>0, Scalp IGA>0, and pp-IGA>0, respectively. The categorization of whether or not subjects had prior exposure to biologic therapy will be based on the Psoriasis Treatment History CRF module. Prior anti-TNFs include etanercept, adalimumab, infliximab, certolizumab pegol, and golimumab.

By-subject listings of Baseline characteristics will be provided.

6.3 Medical history and concomitant diseases

Previous and ongoing medical history will be summarized by treatment group(s), system organ class (SOC) and preferred term (PT) using MedDRA[®]. Medical procedures are not coded.

The following listings for medical history and concomitant diseases will be provided: medical history, psoriasis history, concomitant medical procedures, previous and ongoing medical history glossary, previous and ongoing medical history conditions, and procedure history.

6.4 Prior and concomitant medications

Medication start and stop dates will be compared to the date of first dose of treatment to allow medications to be classified as either Prior or Concomitant.

Details of imputation methods for missing or partial dates are described in Section 4.2.2.

Prior medications include any medications that started prior to the start date of study medication.

Concomitant medications are medications taken at least one day in common with the study medication dosing period.

The number and percentage of subjects taking prior medications (excluding past psoriasis medications) will be summarized by treatment group, overall and by Anatomical Therapeutic Chemical classification (ATC) class, presenting Anatomical Main Group (ATC Level 1), Pharmacological Subgroup (ATC level 3), and preferred term. The number and percentage taking concomitant medications will be summarized similarly.

Past psoriasis medications will be captured separately and will also be summarized by treatment group. These medications are not subject to dictionary coding. In addition, subjects who failed past psoriasis biologic treatment will be summarized by reason of failure as captured on the Psoriasis Treatment History CRF module.

By-subject listings of all Prior and Concomitant medications, prior and concomitant medications glossary, and psoriasis treatment history will be provided.

7 MEASUREMENTS OF TREATMENT COMPLIANCE

Due to the method of administration of the treatments, compliance will be examined in terms of completed injections.

Treatment compliance will be calculated as:

$$\frac{\text{total number of completed injections}}{\text{total number of expected injections}} \times 100$$

where the total number of expected injections is derived relative to when the subject finishes treatment. In this study, bimekizumab, adalimumab, or placebo are administered according to the schedule in [Table 7-1](#).

It is expected that a subject should complete a total of 40 injections by the end of study. If a subject discontinues early, then the number of expected injections is based on the time of early discontinuation relative to the dosing visits. For example, if a subject discontinues after Week 8 visit and prior to Week 9 visit, the total number of expected injections will be 10.

Percent treatment compliance will be described with summary statistics and categorized as <75% and $\geq 75\%$, by treatment group and study periods (through Week 24 for SS, and through initial and maintenance treatment period for BKZ Set).

A by-subject listing of treatment compliance will be provided.

Table 7–1: Dosing Scheme

7Week Dose Assignment	0	1, 3	4	5, 7	8	9, 11	12	13, 15	16	17, 19	20	21, 23	24	28	32	36	40	44	48	52
bimekizumab 320mg Q4W/Q4W	●●	○	●●	○	●●	○	●●	○	●●	○	●●	○	●●	●●	●●	●●	●●	●●	●●	●●
bimekizumab 320mg Q4W/Q8W	●●	○	●●	○	●●	○	●●	○	●●	○	○○	○	●●	○○	●●	○○	●●	○○	●●	○○
Adalimumab 40mg / bimekizumab 320mg Q4W	▲▲	▲	○○	▲	○○	▲	○○	▲	○○	▲	○○	▲	●●	●●	●●	●●	●●	●●	●●	●●

Q4W=every 4 weeks; Q8W=every 8 weeks

Notes: A bimekizumab 160mg injection is depicted by a black circle (●). A placebo injection is depicted by a white circle (○). An adalimumab 40mg injection is depicted by a black triangle (▲)

8 EFFICACY ANALYSES

All efficacy analyses will be performed on the RS unless otherwise specified.

For efficacy endpoints tested through initial treatment period, comparisons will be made between BKZ Total (pooling the two identical treatment arms prior to week 16) and ADA treatment groups.

For by visit summaries, results will be presented by each individual treatment group as well as BKZ Total group (BKZ 320mg Q4W and BKZ 320mg Q4W/Q8W combined). Change from Baseline will be summarized through initial and maintenance treatment period for BKZ treatment groups; while for the ADA group, the change from baseline will only be summarized up to Week 24.

Additional summaries through the initial and maintenance treatment period will be produced for subjects who received bimekizumab from Week 24 onwards (BKZ week 24 set) in all three randomized treatment groups.

In addition, for subjects who started with adalimumab and switched treatment at the Week 24 Visit, change from Baseline (at Week 24) will be evaluated from Week 28 to Week 56 for PASI score and DLQI score only (see Section 3.2).

8.1 Statistical analysis of the co-primary efficacy variables

8.1.1 Derivations of co-primary efficacy variables

For missing PASI and IGA assessments at Week 16, available data from all visits (unscheduled or scheduled but without a planned assessment) within the 3 days window will be included.

8.1.1.1 Psoriasis Area and Severity Index (PASI)

PASI90 is defined to be equal to 1 if the percentage improvement from Baseline in the PASI scores is 90% or greater and 0 if the percentage improvement from Baseline is less than 90%. This definition is introduced for the purpose of identifying subjects who respond to the treatment (1 = responder, 0 = non-responder).

PASI scoring of psoriatic plaques is based on three criteria: redness (R), thickness (T), and scaliness (S). Severity is rated for each index (R, S, T) on a 0-4 scale (0 for no involvement up to 4 for very marked involvement). The body is divided into four areas comprising the head (h), upper extremities (u), trunk (t), and lower extremities (l). In each of these areas, the fraction of total surface area affected is graded on a 0-6 scale (0 for no involvement; up to 6 for 90% - 100% involvement).

The various body regions are weighted to reflect their respective proportion of BSA. The composite PASI score is then calculated by multiplying the sum of the individual-severity scores for each area by the weighted area-of-involvement score for that respective area, and then summing the four resulting quantities as follows (note for R, T, and S scores are as follows: 0 = none, 1 = slight, 2 = moderate, 3 = marked, and 4 = very marked):

$$\text{PASI} = (0.1 \times (R_h + T_h + S_h) \times A_h) + (0.2 \times (R_u + T_u + S_u) \times A_u) \\ + (0.3 \times (R_t + T_t + S_t) \times A_t) + (0.4 \times (R_l + T_l + S_l) \times A_l)$$

where

R_h, R_u, R_t, R_l = redness score of plaques on the head, upper extremities, trunk, and lower extremities, scored 0-4 respectively;

T_h, T_u, T_t, T_l = thickness score of plaques on the head, upper extremities, trunk, and lower extremities, scored 0-4 respectively;

S_h, S_u, S_t, S_l = scaliness score of plaques on the head, upper extremities, trunk, and lower extremities, scored 0-4 respectively;

A_h, A_u, A_t, A_l = numerical value translation of % area of psoriatic involvement score for the head, upper extremities, trunk, and lower extremities, respectively (where 0 = 0% [clear], 1 = >0% to <10%, 2 = 10% to <30%, 3 = 30% to <50%, 4 = 50% to <70%, 5 = 70% to <90%, and 6 = 90% to 100%).

The highest potential PASI score is 72 for severe disease; the lowest is 0 for no psoriasis lesions. PASI scores are treated as continuous. The percent improvement in PASI scores from Baseline will be computed as:

$$\text{Percent improvement from Baseline} = 100 \times \frac{\text{Baseline PASI} - \text{Post Baseline PASI}}{\text{Baseline PASI}}$$

If a subject has experienced an improvement, this measure will be positive. If a subject has experienced a worsening in their condition, this measure will be negative.

If a subject is missing 1 or 2 severity measurements for a certain region, the average of the remaining severity measurement(s) within that region will be utilized to substitute for the missing severity measurement(s) in that region. If the area of affected skin and/or all severity measurements for up to 2 regions are missing, then the missing (R+T+S) x A for a region will be substituted by the average of the available (R+T+S) x A. Otherwise, the PASI will be set to missing.

8.1.1.2 PASI90 Response at Week 16

A categorical response variable, PASI90 at Week 16 is defined to be equal to 1 if the percentage improvement from Baseline to Week 16 in the PASI scores is 90% or greater and 0 if the percentage improvement from Baseline to Week 16 is less than 90%. This definition is introduced for the purpose of identifying subjects who respond to the treatment (1 = responder, 0 = non-responder).

8.1.1.3 Investigator's Global Assessment (IGA) Response at Week 16

A static IGA for psoriasis will be used to assess disease severity in all subjects during the study.

The Investigator will assess the overall severity of psoriasis using the following five-point scale:

Table 8–1: Investigator’s Global Assessment

Score	Short Descriptor	Definition
0	Clear	No signs of psoriasis; post-inflammatory hyperpigmentation may be present
1	Almost clear	No thickening; normal to pink coloration; no to minimal focal scaling
2	Mild	Just detectable to mild thickening; pink to light red coloration; predominately fine scaling
3	Moderate	Clearly distinguishable to moderate thickening; dull to bright red, clearly distinguishable to moderate thickening; moderate scaling
4	Severe	Severe thickening with hard edges; bright to deep dark red coloration; severe/coarse scaling covering almost all or all lesions

IGA response is defined as clear [0] or almost clear [1], with at least a 2-category improvement from Baseline at Week 16.

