4.2 Handling of dropouts or missing data

4.2.1 Handling of missing data for efficacy variables

Based on previous studies of biologics in subjects with moderate to severe chronic plaque psoriasis, it is expected that the number of subjects who discontinue prior to Week 16 will be low. For the small percentage of subjects for whom primary endpoint data are unavailable at Week 16, this lack of data is suggestive of an ineffective study treatment, thereby supporting the imputation of non-response. Achieving the clinical response and making it through 16 weeks of study treatment are both critical components of the primary outcome. Therefore, non-responder imputation (NRI) will be used as the method for handling missing data in the primary analysis for binary efficacy variables.

If a subject discontinued study treatment without terminating from the study and still continues with scheduled assessments, all efficacy data after last treatment date + 35 days will be treated as missing and subject to imputation as applicable.

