$$SE_{MH} = \sqrt{\frac{\sum_i \left\{ \frac{[a_i * c_i * (b_i + d_i)^3] + [b_i * d_i * (a_i + c_i)^3]}{(a_i + c_i) * (b_i + d_i) * n_i^2} \right\}}{\left\{ \sum_i \left[\frac{(a_i + c_i) * (b_i + d_i)}{n_i} \right]^2 \right\}}}$$

$$CI_{MH} = RD_{MH} \pm \text{probit}(1 - (\alpha/2)) * SE_{MH}$$

For the assessment of non-inferiority of bimekizumab to adalimumab, the lower 97.5% confidence limit for the stratified Mantel-Haenszel risk difference will be considered. If that value is greater than -10%, then non-inferiority will have been established.

Non-responder imputation will be used to account for missing data in the primary analysis. Specifically, any subject who withdraws from IMP prior to Week 16 or who has missing data for the co-primary efficacy variables at the Week 16 time point will be considered as a non-responder.

The number and percentage of subjects who are PASI90 responders at Week 16 will be summarized. IGA response will be summarized in the same manner as PASI90 responder variable.

A line plot of the percentage improvement from Baseline in PASI score over time by treatment group will be produced.

By-subject listings of PASI and IGA responder variables, PASI and IGA data will be provided.

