8.3.9 Modified Nail Psoriasis Severity Index (mNAPSI) score

Psoriatic nail disease will be evaluated at the Baseline visit using the mNAPSI. All affected nails will be scored (0 to 3) for onycholysis/oil drop dyschromia, nail plate crumbling, and pitting and will be scored (0 for “no” or 1 for “yes”) for leukonychia, nail bed hyperkeratosis, splinter haemorrhages and red spots in the lunula. The score for an individual nail ranges from 0 to 13 with higher scores indicative of more severe nail disease. The total mNAPSI score is the sum of the scores for each individual nail. If a nail is unaffected, it will be recorded as such and will not contribute to the total mNAPSI score.

If any of the 7 response items that contribute to mNAPSI is present, while other items are missing (ie, partial mNAPSI data), then the missing items are assumed to be 0 for the mNAPSI calculation. In some cases, the data may be captured in such a way that only non-zero component scores are present in the database. Again, those components that are not present are simply assumed to be 0 for the mNAPSI calculation.

Change from Baseline in mNAPSI score for subjects with nail PSO at Baseline is defined as Post-Baseline mNAPSI score minus Baseline mNAPSI.

An mNAPSI75 responder is defined as a subject who achieved at least a 75% improvement from Baseline in the mNAPSI score. mNAPSI90 and mNAPSI100 are defined accordingly. The proportion of mNAPSI75/90/100 responders over time will be summarized for each treatment group.

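### The PASI missing-component rule makes no exception for a region with recorded area grade 0, so a clear region with blank severities can be scored as diseased or can make the whole PASI missing

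*SAP*

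**What the plan says.** SAP 8.1.1.1 computes PASI as a weighted sum over head, arms, trunk and legs (weights 0.1, 0.2, 0.3, 0.4) of the product (R+T+S) x A. R, T and S are severity scores from 0 to 4, and A is an area grade from 0 (clear) to 6.

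The rule for missing components has three tiers:

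- **Within a region.** "If a subject is missing 1 or 2 severity measurements for a certain region", the mean of the remaining severities in that region is used.
- **Whole regions.** The condition is "If the area of affected skin and/or all severity measurements for up to 2 regions are missing". The consequence, which takes a plain unweighted mean, is worded as follows: "then the missing (R+T+S) x A for a region will be substituted by the average of the available (R+T+S) x A".
- **More than two regions.** "Otherwise, the PASI will be set to missing".

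A missing Week 16 PASI then leads to non-response. SAP 8.1.2 applies non-responder imputation (NRI) to "any subject who withdraws from IMP prior to Week 16 or who has missing data for the co-primary efficacy variables".

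For nail disease, SAP 8.3.9 foresees that "the data may be captured in such a way that only non-zero component scores are present in the database" and sets absent components to 0. SAP 8.1.1.1 has no such sentence for PASI.

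**The concern.** The second tier is triggered when all severities of a region are missing, even if its area grade was recorded. When that grade is 0, nothing is unknown, because the product is 0 whatever the severities are. Read literally, the rule replaces this known 0 with an average of diseased regions, or counts the region towards the limit of two.

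PASI90 at Week 16 is co-primary. PASI75 at Week 4, PASI100 at Weeks 16 and 24 and PASI90 at Week 24 are secondary comparisons with adalimumab. All of them use this derivation. The subjects exposed are those with several cleared regions, which are the subjects these endpoints are meant to identify.

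The planned missing-data analyses would show only part of the problem. An inflated PASI is a non-missing value, so the multiple-imputation, observed-case and LOCF analyses in SAP 8.1.3 would accept it. Only the cases set to missing would be handled differently by those analyses.

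**Working it through.** **Inputs.** Weights, area grades, substitution rule and PASI90 definition: SAP 8.1.1. PASI100: SAP 8.2.1.1. NRI: SAP 8.1.2. Entry minimum of PASI 12: protocol 6.1. Planning rates: protocol 14.9 and SAP 2.4. The Baseline of 20.1 is an illustration, with area grade 3 everywhere, severities 2,2,2 on head and arms (product 18) and 3,2,2 on trunk and legs (product 21): 0.1x18 + 0.2x18 + 0.3x21 + 0.4x21 = 20.1.

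**Size of the inflation.** If one or two regions are clear (A = 0) with blank severities, the rule adds (sum of the weights of the blank regions) x (mean of the available products). This is above 0 only if there is disease elsewhere.

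**Case 1: all four regions clear.** With blanks in 0, 1 or 2 regions, the available products are all 0 and PASI = 0. With blanks in 3 or 4 regions, PASI is missing and the subject is a non-responder.

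**Case 2: head and arms clear and blank.** Trunk severities 1,1,0 with A = 1 give product 2. Leg severities 1,1,1 with A = 1 give product 3.
- Known value: 0.3x2 + 0.4x3 = 1.80. Improvement (20.1 - 1.80)/20.1 = 91.0%, a PASI90 responder.
- Rule: mean of 2 and 3 is 2.5, so 1.80 + (0.1 + 0.2)x2.5 = 2.55. Improvement 17.55/20.1 = 87.3%, not a responder.

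**Case 3: as case 2, but only the arms are blank** (head recorded as 0). The mean of 0, 2 and 3 is 1.667, so PASI = 1.80 + 0.2x1.667 = 2.13. Improvement 17.97/20.1 = 89.4%. One blank region is enough to lose PASI90.

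**Case 4: Baseline at the entry minimum of 12.** Head and arms clear and blank, trunk product 1, leg product 2.
- Known value: 0.3 + 0.8 = 1.10, improvement 90.8%.
- Rule: 1.10 + 0.3x1.5 = 1.55, improvement 87.1%.

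**Case 5: three clear regions blank, leg product 1.** The known PASI is 0.4, which is 98.0% improvement from 20.1. The rule sets PASI to missing, hence non-response.

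**PASI100.** Inflation needs disease elsewhere, so such a subject is not a PASI100 responder anyway. PASI100 can be lost only by the missing-score route, with three or four blank regions.

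**With the exception (A = 0 gives product 0)** the scores are 0, 1.80, 1.80, 1.10 and 0.4, each equal to the known value.

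**Scale for the trial.** The plan gives no figure for this rule. Its nearest figure is the PASI90 power: 75% v 50%, 300 v 150 subjects, two-sided 0.05.
- Pooled rate (150x0.50 + 300x0.75)/450 = 0.667. Null SE = sqrt(0.667 x 0.333 x (1/150 + 1/300)) = 0.0471. Alternative SE = sqrt(0.25/150 + 0.1875/300) = 0.0479.
- Power = Phi((0.25 - 1.96x0.0471)/0.0479) = 99.95%, which reproduces the stated value of above 99%.

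The documents give no frequency, so the loss fractions below are assumptions:

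| Share of PASI90 responders lost | Both arms | Bimekizumab only |
|---|---|---|
| 2% | 99.9% | 99.8% |
| 5% | 99.8% | 99.3% |
| 10% | 99.6% | 94.8% |
| 20% | 98.2% | 52.3% |

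**The case against.** **The rule may already mean the right thing.** The operative clause replaces a missing product, and with A = 0 the product is not missing. This reading is fair, but the trigger clause names missing severities as sufficient in themselves. Two programmers could derive different scores from the same record, so the ambiguity stands.

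**Zeros are probably entered.** Protocol 9.1 has redness, thickness and scaliness rated in each body area, with 0 for none, so a clear region has a defined entry. The nail instrument is a weak analogy, because it scores affected nails only. Protocol 13.3.2 adds data-cleaning checks and manual review. All of this lowers the likely frequency. But protocol 9.1 asks for the average severity of lesions, a clear region has none, and neither document says that 0 must be entered.

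**Other safeguards exist.** Assessments within 3 days can stand in for a missing Week 16 PASI (SAP 8.1.1), and a complete Screening score can replace an incomplete Baseline score (SAP 3.2). Neither corrects an inflated post-Baseline score, and neither covers Week 4 or Week 24.

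**A reader might infer a larger fault.** If trunk and legs (0.3 + 0.4 = 70% of the weight) are unscored and head and arms are clear, the rule returns PASI 0 and a PASI100 responder. That can look like a breach of the plan's premise that "this lack of data is suggestive of an ineffective study treatment, thereby supporting the imputation of non-response". The documents do not support calling it a breach. Protocol 14.7 leaves partial-component rules to the SAP and applies NRI where a variable is completely missing, or is treated so under those rules. The substitution can also err the other way. From regional products 12, 21, 21 and 32 (Baseline 24.5), suppose head and arms are clear but wholly unscored, with trunk product 2 and leg product 4. The true PASI is 2.2 (91.0%), and the rule gives 3.1 (87.3%). Barring substitution for responder endpoints would make one blank head area grade (10% of the weight) force non-response. The same subject would also have a PASI for the continuous summaries but not for response. How much partial data to accept is a design choice about a rare event.

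**Conclusion.** The point holds as a defect in a stated derivation: where area grade 0 is recorded, the rule as worded can override a value that the formula already determines. One or two clear regions with blank severities can cost a subject PASI90. Three or four can cost PASI90 and PASI100 through NRI.

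The size rests on one fact that the documents do not give, namely whether severities are recorded as 0 or left blank when a region is clear. If 0 is always recorded, the effect is nil. Because the planning assumptions expect more PASI90 responders on bimekizumab (75% v 50%), post-Baseline losses would probably fall more on that arm and be conservative for both noninferiority and superiority. It would be wrong to infer that the rule favours bimekizumab or that power is under threat. Equal proportional losses of up to 20% in both arms leave PASI90 power at 98.2%, and the lower figures need losses confined to bimekizumab, which nothing in the documents indicates.

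**What to change.** Add to SAP 8.1.1.1, ahead of the substitution rule: the regional product is set to 0 for every region with a recorded area grade of 0, whether or not its severities are recorded. A region counts as missing only if its area grade is not recorded, or if its area grade is above 0 and all three severities are missing. The rest of the rule can stay.

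The cost is two sentences and one step in the derivation program, made before unblinding. There is no statistical trade-off, because the step only applies the PASI formula. If the eCRF already enforces zeros, no score changes.

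Optionally, list every responder whose PASI used a substituted region. That would show how often scores rest on unassessed regions without changing the endpoint.
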